- v. The study team will monitor, document and report to the Institutional Review Board, any adverse events among study participants per the plan detailed below.

Reportable Events

The PI at each site will oversee the safety of the study at his/her site. During the study, the investigator or study site personnel will be responsible for querying and recording adverse events (AEs) and serious adverse events (SAEs), as detailed below.

Types of Reportable Events:

Serious Adverse Events (SAE)

The site must report all SAEs to the lead site, whether or not they result from study participation, within 24 hours of learning of the event. A serious adverse event (SAE) is any adverse event occurring within the timelines specified in the protocol that results in any of the following outcomes:

- Death
- Life-threatening situation (subject is at immediate risk of death)
- Inpatient hospitalization or prolongation of existing hospitalization
- Persistent or significant disability/incapacity
- Congenital anomaly/birth defect in the offspring of a subject who received study drug
- Important medical events that may not result in death, be immediately life-threatening, or require hospitalization, may be considered an SAE when, based upon appropriate medical judgment, they may jeopardize the subject and may require medical or surgical intervention to prevent one of the outcomes listed in this definition.

Adverse Events (AE)

An adverse event is any untoward medical occurrence in a clinical investigation subject administered an investigational product and which does not necessarily have to have a causal relationship with this treatment. An AE can, therefore, be any unfavorable and unintended sign (that could include a clinically significant abnormal laboratory finding), symptom, or disease temporally associated with the use of a medicinal product, whether or not considered related to the medicinal product.

For this study, abnormal laboratory findings (e.g., clinical chemistry, hematology) or other abnormal assessments (e.g., electrocardiogram, X-rays, vital signs) per se are not reported as AEs. Only the Adverse Events of Special Interest (AESI) defined below will be recorded on the CRFs and in the subject's chart.

Adverse Events of Special Interest (AESI)

Adverse events of particular clinical importance (other than SAEs mentioned above) will be classified as adverse events of special interest (AESIs). For this study, AESIs refer to:

• Mild/moderate reactions:

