- venipuncture complications (blood clot or infection)
- o bowel changes (constipation or diarrhea)
- chest tightness
- itching
- o urticaria
- flushing
- o nausea/vomiting
- o abdominal pain
- o peripheral edema
- arthralgia
- o new onset back or joint aches
- o mild shortness of breath
- tachycardia
- o severe hypertension (For infusion group: confined to infusion timeframe only)
- o severe hypotension (For infusion group: confined to infusion timeframe only)
- o neurological changes (syncope, dizziness, headache) (For infusion group: confined to infusion timeframe only)

Major reactions:

- o anaphylaxis-like reaction (For infusion group: confined to infusion timeframe only)
- o seizures (For infusion group: confined to infusion timeframe only)
- o non-reassuring fetal heart rate tracing (For infusion group: confined to infusion timeframe only)

Assessing and Documenting Reportable Events:

Subjects will be evaluated for adverse events in the following manner:

- Routine monitoring by infusion nurses during the IV iron treatment, with data obtained from the subject's EMR by research staff.
- Subjects will be called by research staff 48-72 hours after infusion to assess for transfusion reactions.
- Subjects on oral iron therapy will be monitored via their EMR and via contact with research staff as outlined in schedule of events

An adverse event report will be generated for each event that will include the following:

- Date of event discovery
- Severity (mild, moderate, severe, life threatening/disabling, death)
- Relationship to treatment
- Action taken
- Outcome
- Expected or not
- Date reported
- Relevant notes/chart records/supporting documentation to corroborate the event
- To whom event was reported (i.e. IRB, lead site, etc.)
 - Non- serious AESIs will be reported to the lead site within 5 days of discovery, and to the IRB at renewal.
 - SAEs and SAESIs will be reported within 24 hours of discovery to the IRB and the lead site.

Relationship of Reportable Events:

An investigator must make the determination of relationship to the drug for each SAE and/or AESI. The relationship to the drug should be assessed using the guidelines presented in the table below.

Relationship to Drug	Description
Related	Previously known toxicity of agent; or
	 Follows a reasonable temporal sequence from administration of the drug; or
	• Follows a known or expected response pattern to the suspected intervention; or

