Confidentiality:

Information about study subjects will be kept confidential and managed according to the requirements of the Health Insurance Portability and Accountability Act of 1996 (HIPAA). Those regulations require a signed subject authorization informing the subject of the following:

- What protected health information (PHI) will be collected from subjects in this study
- Who will have access to that information and why
- Who will use or disclose that information
- The rights of a research subject to revoke their authorization for use of their PHI

In the event that a subject revokes authorization to collect or use PHI, the investigators, by regulation, retain the ability to use all information collected prior to the revocation of subject authorization. For subjects that have revoked authorization to collect or use PHI, attempts should be made to obtain permission to collect at least vital status (i.e. that the subject is alive) at the end of their scheduled study period.

DATA COLLECTION AND MANAGEMENT

Case Report Forms

Qualified study staff at the investigational site will perform primary data collection. Electronic case report forms (eCRFs) will be used to collect all subject data during the study. The investigator is responsible for the accuracy and completeness of all data on the eCRFs. Lead site personnel will review completed eCRFs at regular intervals throughout the study.

Information on the eCRFs will be compared to information originally recorded on source documents related to the study. Information on the eCRF must match the same information on the source documents or a data query will be issued. All eCRFs will be reviewed for completeness, validity, and consistency. Queries will be generated and resolved with the sites and all protocol deviations will be recorded on the eCRF.

Source Data and Documents

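### The plan does not clearly put SAEs on the case report forms, sets no SAE collection period, and lists different adverse event evaluation in the two arms

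*Combined protocol and SAP*

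**What the plan says.** The relevant text is under Reportable Events and in the Case Report Forms section.

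- **What is recorded.** The Adverse Events (AE) paragraph first sets aside abnormal laboratory and other test findings. It then states: "Only the Adverse Events of Special Interest (AESI) defined below will be recorded on the CRFs"; the same sentence applies this limit to the participant's chart as well.
- **What an AESI is.** The next paragraph reads: "Adverse events of particular clinical importance (other than SAEs mentioned above) will be classified as adverse events of special interest (AESIs").
- **What the eCRFs hold.** Case Report Forms says: "Electronic case report forms (eCRFs) will be used to collect all subject data during the study".
- **When an event counts as an SAE.** The definition is "any adverse event occurring within the timelines specified in the protocol that results in any of the following outcomes".
- **How SAEs are reported.** Site staff are "responsible for querying and recording adverse events (AEs) and serious adverse events (SAEs), as detailed below". Each site "must report all SAEs to the lead site, whether or not they result from study participation", within 24 hours. Under Assessing and Documenting Reportable Events, "An adverse event report will be generated for each event that will include the following", followed by fields such as severity, relationship and outcome.
- **How events are found.** The same section lists nurse monitoring during the infusion (with data taken from the EMR) and a call at 48-72 hours for the intravenous arm. For the oral arm it lists EMR monitoring plus the contacts in Figure 2, which fall 2-4 weeks after randomization and at delivery.

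**The concern.** Safety is half of the stated objective, and the trial is open-label. A comparison of serious events between arms needs three things: a common definition of what is recorded, a common period at risk, and the same effort to find events in each arm. The text leaves the first contradictory, omits the second, and describes the third differently by arm.

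The protocol refers to a principal investigator at each site, so different sites may resolve these gaps differently. A difference in SAE counts, or the lack of one, could then reflect recording practice rather than treatment. The annual report described under Data Monitoring and Quality Control meets the same difficulty. It is to judge whether adverse event rates match pre-study assumptions, but a rate without a defined period has no clear denominator.

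**Working it through.** The plan states no figure on this point, so there is nothing to reproduce. The check is a comparison of the passages.

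**Step 1. Is there an SAE window?** The times given in the protocol are:

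- reporting deadlines: 24 hours for SAEs, 5 days for non-serious AESIs;
- contact times: 48-72 hours after infusion, 2-4 weeks after randomization, delivery;
- an infusion timeframe attached to some AESIs, which is itself not defined.

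None of these is a start or an end for SAE collection. The cross-reference in the SAE definition has no target.

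**Step 2. Which serious events reach the CRF?** The AESI-only sentence can be read in three ways. The term SAESI, used in the reporting rules, implies that a listed reaction can be serious and still be an AESI, which gives reading B.

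| Reading | Serious event | Oral arm | Intravenous arm |
|---|---|---|---|
| A. AESIs exclude all SAEs | any | off CRF | off CRF |
| B. Serious listed reactions remain AESIs | seizure weeks after treatment starts | on CRF | off CRF |
| B. As above | event not on the AESI list | off CRF | off CRF |
| C. Sentence limits non-serious AEs only | any | on CRF | on CRF |

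The asymmetry under B comes from the AESI list. Six entries carry a limit to the infusion timeframe for the infusion group: severe hypertension, severe hypotension, neurological changes, anaphylaxis-like reaction, seizures, and non-reassuring fetal heart rate tracing. The oral arm has no such limit. A seizure some weeks after randomization is therefore an AESI in the oral arm and is not one in the intravenous arm.

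Only reading C agrees with the Case Report Forms section. The text does not say that C is intended.

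**Step 3. Are events looked for equally?** Even under C, an event must be found before it is recorded. After the 48-72 hour call, the evaluation list names nothing further for the intravenous arm. For the oral arm it names EMR monitoring and contacts up to delivery. Figure 2 does schedule chart abstraction of delivery and neonatal outcomes with no restriction by arm. That covers outcomes around birth, but it is not described as a search for SAEs between infusion and delivery.

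**Step 4. Is a comparison planned?** The Data analysis section gives general tests for continuous and categorical variables. It does not mention SAEs or a tabulation of them by arm.

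**The case against.** The strongest defence is that SAEs are captured by another route. Staff must query and record them, every SAE goes to the lead site within 24 hours whatever its cause and in either arm, each event gets its own report, and the outcome categories expressly cover SAEs. The AESI-only sentence sits under the AE heading, directly after the laboratory exclusion, and so may be meant for non-serious events alone. Read strictly, it would also keep SAEs out of the participant's chart, although chart records are to support the event reports. The prespecified safety outcome is infusion reactions. Transfusion, readmission and neonatal morbidities are separate outcomes in both arms.

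Much of this stands, and it rules out several stronger inferences that a reader might draw:

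- *That SAE counts cannot be produced or compared by arm.* The lead site would hold a report on every reported SAE and could tabulate these by arm.
- *That SAE capture in the intravenous arm ends at the 48-72 hour call, so that the ratio of time at risk can be calculated.* Nothing ties SAE capture to that call, whose stated purpose is to ask about reactions. The SAE criteria include a birth defect in a treated participant's child, which would usually be established only at birth. Any such ratio would rest on a rule that the protocol does not contain.
- *That every delivery admission becomes an SAE.* An SAE must first be an untoward occurrence, and an uncomplicated delivery is not one.
- *That the eCRF lacks an SAE page.* The forms are not in the documents, so this cannot be checked.

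The defence does not supply the missing window. The 24-hour reports inherit it, because what qualifies as an SAE depends on it. Nor does the defence equalize the listed evaluation or remove the conflict over what goes on the CRF.

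**Conclusion.** The point holds as a defect of recording and ascertainment. The rule on what goes on the CRFs contradicts the Case Report Forms section, the SAE definition refers to timelines that do not exist, and the evaluation and AESI rules differ by arm. On at least one reasonable reading, the same late serious event is on the CRF in the oral arm and off it in the intravenous arm. SAE counts by arm can be assembled from the reports, but they would be open to unequal ascertainment and hard to interpret.

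No numerical size is given. The documents state no expected SAE rate and no window from which to calculate one. The primary outcome, the sample size and the infusion-reaction outcome during treatment do not depend on this point. The conclusion assumes that sites follow the text as written and that no other instruction to sites, outside these documents, sets the window. The correction should be made because safety is a stated objective and the change is cheap.

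**What to change.** 1. **Reconcile the recording rule.** Amend the Adverse Events (AE) paragraph to agree with Case Report Forms, for example: *All SAEs, and the AESIs listed below, will be recorded on the eCRF in both arms.* State that a listed reaction which is serious is recorded as an SAE whenever it occurs within the collection period, whatever timeframe limit applies to it as an AESI.
2. **Set one SAE collection period.** Replace the reference to protocol timelines with a single start and end that apply to both arms, for example randomization to discharge from the delivery hospitalization. Readmission is a listed maternal outcome; if readmissions are to count as SAEs, the period must run past discharge.
3. **Equalize ascertainment.** Specify the same search for SAEs in both arms, for example an EMR review at delivery covering the whole period, and add it to Figure 2.
4. **Plan the table.** Add to Data analysis a tabulation of SAEs by randomized arm, giving participants with at least one SAE and the number of events.

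A sentence stating that an uncomplicated delivery admission is not an SAE would be a useful but optional clarification.

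The cost is a few sentences of protocol text and a small amount of extra data entry and chart review. The reports themselves are already required within 24 hours. If enrollment has begun, SAEs already reported can be entered from the existing reports and the EMR review applied to participants who have already delivered.

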Overview: We will conduct an open-label, randomized controlled trial to assess the effectiveness and safety of treating iron-deficiency anemia in pregnant women with intravenous iron compared with oral iron. We test the *hypothesis* that treating iron-deficiency anemia with intravenous iron is associated with improved maternal and neonatal outcomes compared with oral iron. We will use broad inclusion criteria and analyze data using the intention-to-treat principle to increase generalizability of the findings.

Inclusion & exclusion criteria:

Inclusion criteria:

- Pregnant women
- 18 years or older
- Diagnosed with iron-deficiency anemia
 - Serum ferritin <30ug
 - o Hgb <10 g/dl
- Between 24 34 weeks gestation
- Plan to deliver at an in-network hospital
- Able and willing to give informed consent

Exclusion criteria:

- Diagnosis of non-iron-deficiency anemia
- Multiple gestation
- Known or suspected major fetal anomaly or aneuploidy
- Planned delivery at out-of-network hospital
- Unable or unwilling to give consent

Study outcomes:

Primary outcome: The primary outcome of the trial is maternal anemia, defined as Hgb <11mg/dl, on admission for labor and delivery.

Secondary outcomes:

- 1. Safety:
 - i. Mild/moderate infusion reactions: chest tightness, itching, urticaria, flushing, nausea/vomiting, arthralgia, back or joint aches, mild shortness of breath, tachycardia, hypertension or hypotension, abdominal pain, diarrhea, peripheral edema, headache, dizziness, syncope, or numbness.
 - ii. Major infusion reaction: anaphylaxis-like reaction, seizures, or non-reassuring fetal heart rate tracing.

2. Maternal outcomes:

- i. Hgb at admission to labor and delivery
- ii. Hgb on postpartum day 1
- iii. Ferritin at admission to labor and delivery
- iv. blood transfusion
- v. mode of delivery
- vi. postpartum disposition
- vii. readmission

3. Neonatal outcomes

- i. gestational age at delivery
- ii. birth weight
- iii. cord gases (if performed as SOC)
- iv. umbilical artery lactate (if performed as SOC)
- v. APGAR scores
- vi. Hgb (obtained from cord blood)
- vii. Ferritin (obtained from cord blood)
- viii. neonatal morbidities
- ix. postpartum disposition

Screening:

[figure not shown]

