	• Is confirmed by stopping or reducing the dosage of the drug; and is not explained by any other reasonable hypothesis
Probably related	Follows a reasonable temporal sequence from the time of study intervention; and/or
	Follows a known response pattern to the study drug; and
	• Was unlikely to have been produced by other factors such as the subject's clinical state,
	therapeutic intervention, or concomitant therapy
Possibly related	Follows a reasonable temporal sequence from the time of study intervention; and/or
	Follows a known response pattern to the study drug; but
	• Could have been produced by other factors such as the subject's clinical state, therapeutic intervention, or concomitant therapy
Unlikely related	• Does not follow a reasonable temporal sequence from the time of study intervention; and
	Was likely produced by other factors such as the subject's clinical state, therapeutic
	intervention, or concomitant therapy but for which relationship cannot be definitely ruled out
Not related	The adverse event can be determined with certainty to have no relationship to the study drug

Severity of Reportable Events:

The investigator will assess the severity of the AE using the following general guidelines:

Severity	Description
Mild:	An AE that is usually transient, requiring no special treatment, and does not interfere with the subject's daily activities.
Moderate:	An AE that introduces a low level of inconvenience or concern to the subject and may interfere with daily activities but is usually ameliorated by simple therapeutic measures.
Severe:	An AE that interrupts a subject's usually daily activity and typically requires systemic drug therapy or other treatment (a severe AE may not necessarily qualify as an SAE).
Life-threatening:	An AE that put the subject at immediate risk of death from the event as it occurred. This does not include an event that might have led to death if it had occurred with greater severity.

Outcomes of Reportable Events:

The investigator will categorize the outcome of each reportable event according to the definitions below:

Status	Description	
Resolved:	The subject recovered from the SAE or AESI.	
Resolved with sequelae:	A condition whereby the consequences of a disease or injury include lingering effects.	

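### The mild/moderate and major safety categories go by symptom name and conflict with the protocol's severity scale, so severe but non-serious infusion reactions can be reported as mild/moderate

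*Combined protocol and SAP*

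**What the plan says.** Four places in the protocol bear on this.

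- **Study outcomes, Secondary outcomes, Safety.** Reactions have two levels, each a list of symptoms. The mild/moderate list ends with "tachycardia, hypertension or hypotension, abdominal pain, diarrhea, peripheral edema, headache, dizziness, syncope, or numbness"; blood-pressure changes and syncope have no severity limit. The upper level is "Major infusion reaction: anaphylaxis-like reaction, seizures, or non-reassuring fetal heart rate tracing". On this list only breathing carries a qualifier: "mild shortness of breath".
- **Reportable Events, Adverse Events of Special Interest (AESI).** Under "Mild/moderate reactions" the list includes "severe hypertension (For infusion group: confined to infusion timeframe only" and "severe hypotension (For infusion group: confined to infusion timeframe only", each with a closing bracket. The major group repeats the same three events as the outcome. The preceding section on adverse events says that abnormal vital signs are not in themselves reported, and that only listed AESIs go on the CRF.
- **Assessing and Documenting Reportable Events.** Each event report carries a severity entry, with severe separate from mild and moderate.
- **Severity of Reportable Events.** Severe is defined as "An AE that interrupts a subject's usually daily activity and typically requires systemic drug therapy or other treatment", with a note that such an event need not qualify as a serious adverse event (SAE).

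No section says how the grade relates to the two outcome levels, or which of them is used to report safety. The Data analysis section gives no tabulation rule for reactions.

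**The concern.** A label of mild/moderate tells the reader that nothing in that row was severe. Here the row can hold events that the investigator graded severe, and two of its AESI lines are severe by their own wording. Meanwhile a brief non-reassuring tracing is major whatever its grade. Safety is half of the stated objective, and the synopsis presents the trial as informing whether intravenous iron should be used more liberally. A report of no major infusion reactions could therefore coexist with severe-graded reactions in the lower row, and a reader of the summary table could not tell.

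**Working it through.** The plan states no reaction rate, so there is no figure to reproduce. The check is to follow individual events through the lists and the scale.

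| Infusion event | Safety outcome | AESI list | Grade it could carry |
|---|---|---|---|
| Hypotension or hypertension, not severe | mild/moderate | not listed | mild or moderate |
| Hypotension or hypertension, severe | mild/moderate (term unqualified) | mild/moderate | severe |
| Syncope, any degree | mild/moderate | mild/moderate | any |
| Shortness of breath, mild | mild/moderate | mild/moderate | mild |
| Shortness of breath, more than mild, not anaphylaxis-like | no level | not listed | moderate or severe |
| Non-reassuring fetal tracing | major | major | any |

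1. *Severe blood-pressure reaction.* Both lists send it to mild/moderate, while the scale makes severe a different grade from either. This is the direct contradiction.
2. *Worse dyspnea.* The Potential Risks section names shortness of breath as an infusion side effect without a qualifier, but both lists cover only the mild form. Because the CRF is limited to listed AESIs, a worse but non-serious case has no line, and later re-tabulation from the CRF could not recover it.
3. *Non-severe blood-pressure reaction.* It counts toward the outcome but has no AESI line, so the outcome and its data source do not match.
4. *Does the SAE route close the gap?* Only in part. AESIs are defined as events other than SAEs, and the scale says that a severe event may not be an SAE. Severe, non-serious reactions remain.

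Count of AESI lines: 16 under mild/moderate and 3 under major, 19 in all. Some of the 16, such as venipuncture complications and constipation, are not infusion reactions in the safety outcome, so 16 of 19 does not measure how much of the outcome is affected.

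Scale, for illustration only. The plan recruits 120 women 1:1, so 120/2 = 60 in the intravenous arm, and one event is 1/60 = 1.7 percentage points. Exact (Clopper-Pearson) 95% intervals:

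- 0/60 = 0% (0 to 6.0%)
- 1/60 = 1.7% (0.0 to 8.9%)
- 2/60 = 3.3% (0.4 to 11.5%)

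If the true rate p of severe, non-serious reactions were as assumed below, the chance of at least one is 1 − (1 − p)^60:

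| Assumed p | Chance of at least one in 60 |
|---|---|
| 0.5% | 26% |
| 1% | 45% |
| 2% | 70% |
| 5% | 95% |

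**The case against.** The strongest reply is that the protocol defines major as three named events, so nothing is miscounted under its own definition; the category is simply narrow, and where to draw that line is a design choice. The word severe appears in the AESI reporting list and not in the outcome, and there it may be meant as a recording threshold, since vital signs alone are not reported. Severe events are graded on each report, serious ones go to the IRB and the lead site within 24 hours, the annual report summarises adverse events, and a reaction in the lower row is still counted as an infusion reaction.

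Much of this stands. A reader might infer that the major-reaction rate is understated and the safety conclusion biased toward intravenous iron. The documents do not show that. It would require such events to occur, not to be classed as anaphylaxis-like, and major to be meant to cover all severe events. A reader might also take the major rate as the figure that decides safety, but the plan sets no safety threshold and no analysis of major reactions alone.

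The reply does not remove the contradiction. The recording-threshold reading is nowhere stated, and it would still leave severe events under a mild/moderate heading. An unqualified term in the outcome covers every degree. The grade helps only if the plan says that it is used, and only for events that have a line on the form.

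**Conclusion.** The point holds as a conflict of classification: the outcome list, the AESI list and the severity scale cannot all be followed and give a coherent safety table. On a literal reading, severe but non-serious infusion reactions are reported as mild/moderate, and some worse dyspnea is not captured. The consequence is that the major count *can* miss severe events; that it does so is not established. No corrected rate can be computed, because the documents give neither event rates nor a definition of severe blood-pressure change. The 1.7 points per event assumes that all of about 60 women allocated to intravenous iron form the denominator. It is worth correcting because the edits are small and safety is a stated aim.

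**What to change.** Reconcile the Safety outcome list, the AESI list and the severity scale, and state which of them defines the reported safety outcome. Specifically:

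- In the AESI list, delete the adjective severe from hypertension and hypotension. In both lists, delete mild from shortness of breath. Keep the lines themselves, so that all degrees are recorded.
- Keep the three named major events as they are.
- Add a tabulation rule: infusion reactions are shown by the severity grade on the event report, and any graded severe or life-threatening is reported as such and never as mild/moderate.
- Limit the rule to infusion reactions. Applied to the whole AESI list, a rule that makes every severe-graded event major would put, for example, severe constipation on oral iron beside anaphylaxis, which changes what the category means.

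The grade is already required on each event report, so the change needs only wording edits and matching form lines. The costs are that the reported number of severe or major reactions may be higher, that the table depends on investigator grading in an open-label trial, and that a few more mild blood-pressure events will be recorded.
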